## ALLOB-DU1 - Clinical Study Protocol

ALLOB-DU1\_CSP

V 05

Author: [name]

February 02, 2017

Pg. 91/136

the patient and documented in source documentation and the CRF. Particularly, the patient must be carefully questioned for the possible occurrence of any AE or SAE.

- *Lack of compliance to the protocol*

The Sponsor has the right to terminate the study at any time.

- *Lost to follow-up*

Intensive efforts will be made to re-contact patients who do not return for scheduled visits in order to, at minimum, determine health status and the potential occurrence of AE and/or SAE. All efforts to re-contact will be documented in the source documentation and the CRF.

- *Lack of efficacy*

Early discontinuation for lack of efficacy will not be considered as an AE but as a treatment failure. The reason of the lack of efficacy will be documented in the CRF and source documents.

- *Other reasons*

If no above-mentioned reasons are applicable in case of early discontinuation, the other reason(s) will be clearly documented and explained in the CRF and source documents.

## 9.2 Procedure for Early Discontinuation

In case of early discontinuation and whenever possible, Investigators will ask patients to perform [REDACTED] Exit Visit as the Premature Discontinuation Visit. At the end of the Exit visit, the Investigator will declare early discontinuation in the CRF. If study participation is terminated due to an AE possibly related to the study medication or trial-related procedures, the subject will however be followed by additional examinations according to the medical judgment of the Investigator until the AE is resolved or the Investigator deems further observations or examinations to be no longer medically indicated. All collected data should be recorded in the source documents and CRF.

## 9.3 Replacement of Subjects

Patients withdrawn from the study will not be replaced.

**ALLOB-DU1 - Clinical Study Protocol**

ALLOB-DU1_CSP	V 05	Author: [name]	February 02, 2017	Pg. 92/136
---------------	------	-------------	-------------------	------------

#### **9.4 Suspension of the Trial**

Overall, the study or the study treatment can be prematurely interrupted in certain circumstances. The Sponsor can stop or interrupt the study for the following reasons:

- ALLOB® is ineffective
- ALLOB® is effective
- Safety issues
- Following a decision of the Competent Authorities or the Ethics Committee.

## ALLOB-DU1 - Clinical Study Protocol

ALLOB-DU1\_CSP

V 05

Author: [name]

February 02, 2017

Pg. 93/136

## 10 STATISTICAL CONSIDERATIONS AND METHODS OF ANALYSIS

A Statistical Analysis Plan (SAP) detailing statistical methods will be generated, reviewed, approved, and signed by the biostatistician, Sponsor and Principal Investigators, prior to first database lock, at the latest. This document will be the main reference as far as statistical analyses are concerned and therefore the description provided in this Protocol will not be exhaustive.

### 10.1 Analysis Populations

Two analysis sets will be defined:

- The safety population that will include all treated patients. (Treated patients will be defined as patients implanted with ALLOB®). As the study is not randomized and only one study group will be studied, the safety set will be used also to analyse the whole efficacy data.
- The Per-Protocol (PP) efficacy population will include all patients of the safety population without any major protocol deviation.

The definition of the populations will be finalised prior to database lock. The safety population will be considered as the primary cohort for the analysis of safety, efficacy, demographics, and baseline characteristics. Efficacy variables will be analysed using the safety population. Primary criteria and corresponding variables will be analysed in the PP population.

The patients screened will be described in the summary table presenting the disposition of patients.

## ALLOB-DU1 - Clinical Study Protocol

ALLOB-DU1\_CSP

V 05

Author: [name]

February 02, 2017

Pg. 95/136

## 10.4 Safety

Safety will be assessed using the following variables:

- AEs
- SAEs
- Vital signs: heart rate and blood pressure
- Physical examination
- Laboratory analyses (haematology and biochemistry)

## 10.5 Statistical Analysis

### 10.5.1 Generality

#### 10.5.1.1 *Descriptive statistics*

Continuous variables will be described using the number of observed values, mean, standard deviation (SD), median, first quartile, third quartile, minimum and maximum values, and number of missing data.

Categorical data will be presented using counts (number and number of non-missing data) and percentages (%). The number of missing data will also be presented. The percentages will be calculated taking into account the non-missing data.

No adjustment on centres is planned.

#### 10.5.1.2 *Type I error rate, significance tests*

In this study, two sided tests will be performed at a 5% level of significance except for efficacy analyses.

According to the Schoenfeld approach (Schoenfeld *et al.*, 1980), for the efficacy analysis, the type I error rate will be increased from the usual 5% to the 10% rate. Indeed, in this pilot single arm “proof of concept” study, it is appropriate to maintain the power and increase the type I error rate. This increases the risk of erroneously concluding that the treatment is worthy of further investigation, but does not increase the risk of missing an efficacious treatment. So in

## ALLOB-DU1 - Clinical Study Protocol

ALLOB-DU1_CSP	V 05	Author: [name]	February 02, 2017	Pg. 96/136
---------------	------	-------------	-------------------	------------

this phase II study, since the trial will be followed by further testings, a type II error may be more serious than a type I error.

#### 10.5.1.3 *Patient dispositions*

All screened and eligible patients will be accounted for. All post-inclusion discontinuations will be summarised and reason for discontinuation. The number of patients screened and not eligible will be presented with the main reason for their non-eligibility.

Patient disposition will be based on the patients screened and tabulated for the following categories:

- Total number of patients enrolled
- Total number of patients eligible
- Number (percentage) of patients completing the study
- Number (percentage) of patients prematurely discontinuing from study
- Primary reason for premature discontinuation
- Number of patients in the safety population
- Number of patients in the PP population

For each population, reasons for exclusion from the population will be carefully described.

#### 10.5.2 *Demographics and patients characteristics*

##### 10.5.2.1 *Demographics and other characteristics*

Descriptive statistics of demographics, and other baseline characteristics as well as medical history will be presented for all eligible patients.

##### 10.5.2.2 *Viral serology*

Viral serology recorded at screening visit will be tabulated.

##### 10.5.2.3 *Fracture characteristics*

Descriptive analysis will be conducted on the Safety and the Per-Protocol population.

**ALLOB-DU1 - Clinical Study Protocol**

ALLOB-DU1_CSP	V 05	Author: [name]	February 02, 2017	Pg. 97/136
---------------	------	-------------	-------------------	------------

The time from fracture to screening, the time from delayed-union diagnosis to screening, fractured bone, fracture side, fracture level, whether the fracture at onset was open, type of fracture, cause of fracture, whether any tendon or nerve was damaged at the fracture site and measure of fracture interline will be summarized.

Time from osteosynthesis to screening, type of osteosynthesis, time from last osteosynthesis revision to screening, and type of osteosynthesis revision will also be presented.

Location of neighbouring bone fracture(s), type of osteosynthesis on the neighbouring bone, whether neighbouring fracture healed and whether a delayed/non-union fracture is on the neighbouring bone will be tabulated.

#### *10.5.2.4 Medical history*

Medical history will be summarised safety population, and frequency of pathologies will be summarised using descriptive statistics. Frequencies will be given by system organ and preferred term according to the MedDRA Dictionary (last available version).

#### *10.5.2.5 Previous and concomitant medications*

Previous and concomitant medications will be summarised for the safety population.

Frequency of medication will be summarised using descriptive statistics:

- frequency of patients with at least one previous medication
- frequency of patients with at least one concomitant medication

Frequency will be given by ATC term according to the WHO Drug Dictionary (WHO DD) (last available version) used for drugs coding. Each frequency table will be sorted by descending frequency of ATC term and then within each ATC by descending frequency of WHO Drug name (all treatment groups).

#### *10.5.3 Protocol deviations*

All the protocol deviations will be identified and acted as major or minor deviations during a data review meeting occurring close to the database lock.

The protocol deviations will be as follows:

- No implantation with ALLOB®

## ALLOB-DU1 - Clinical Study Protocol

ALLOB-DU1_CSP	V 05	Author: [name]	February 02, 2017	Pg. 98/136
---------------	------	-------------	-------------------	------------

- Violation of inclusion/exclusion criteria
- At least one post-inclusion protocol violation (e.g., taking of a forbidden treatment, no evaluation of major efficacy parameters)
- At least one deviation with respect to the study procedure

Frequency and percentages of patients with protocol deviations will be tabulated.

Patients presenting major deviation will be excluded from the PP population.

#### *10.5.4 Implantation procedure*

The whole procedures used for ALLOB® implantation will be summarized descriptively on the all enrolled patients.

These procedures concern:

- If the patient was able to undergo the implantation procedure;
- If the patient had any changes in health occurred since the last visit before implantation;
- If the IMP was released by the sponsor, the pharmacist or the investigator;
- If the implantation was performed;
- the duration of implantation operation;
- In case of a non-implantation, the reasons ;
- The prescribed dose,
- The administered dose and the reason if the prescribed dose was not totally administered;
- If fluoroscopy images were taken;
- If the IMP implantation was performed by the use of 2 different surgical approaches and if yes, the description of the 2 approaches;
- If operative blood loss with the description of the amount;
- Type of anaesthesia;
- Any relevant peri-procedural events.

## ALLOB-DU1 - Clinical Study Protocol

ALLOB-DU1_CSP	V 05	Author: [name]	February 02, 2017	Pg. 99/136
---------------	------	-------------	-------------------	------------

During the 24 hours post-administration follow-up, number of patients having experienced AE/SAE or having done any changes in the concomitant medications will be described.

#### **10.5.5 Extent of exposure**

Extent of exposure will be summarised by descriptive statistics for the duration of treatment, calculated in days as follows:

*Duration of treatment = (Date of last visit or date of rescue surgery – Date of ALLOB® implantation)*

The extent of exposure summary will be presented for the safety and PP populations.

#### **10.5.6 Efficacy analysis**

##### **10.5.6.1 Primary efficacy criteria**

The primary efficacy criteria will be analysed in the safety population and in the PP population, the safety population corresponding to the main efficacy population.

Percentage of responder patients will be calculated as the percentage of patients who will not be considered as failed under treatment at Month 6.

A patient will be considered as failed under a treatment if, at Month 6:

- He/she had a rescue surgery

Or

- The Global Disease Evaluation score (VAS) as perceived by the patient has not improved by at least 25% *and* the TUS as assessed by CT scan has not increased by at least two points (versus baseline).

[REDACTED]

[REDACTED]

[REDACTED]

[REDACTED]

[REDACTED]

ALLOB-DU1 - Clinical Study Protocol

ALLOB-DU1 CSP

V 05

Author: [name]

February 02, 2017

Pg. 100/136

A series of horizontal black bars of varying lengths, likely representing a redacted list of items. The bars are arranged vertically and have irregular, jagged ends, suggesting they are cut-off fragments of a larger list. The lengths of the bars vary significantly, with some being very short and others being quite long.

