**Detailed visit schedule**

After informed consent is obtained, fulfilment of study inclusion and exclusion criteria will be performed at Visit #1, which will take up to 8 weeks to complete. Visit #2 is scheduled to take place after completion of Visit #1 for baseline clinical assessments and ALLOB® implantation (the baseline of the radiological assessments is Visit #1). At Visit #2, all patients will be hospitalized for 24 or 48 hours after implantation, according to the judgment of the Investigator.

Patients will be followed during 6 months, at 2 weeks, 1, 3, and 6 months (Visit #3 to Visit #6).

[REDACTED]

[REDACTED]

[REDACTED]

[REDACTED]

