## 2 INVESTIGATIONAL PLAN

### 2.1 General Study Design

The present study is a prospective, multicentre, open, non-controlled study to assess the safety and efficacy of allogeneic osteoblastic cells (ALLOB®) implantation in non-infected delayed-union fractures.

After signing the Informed Consent Form (ICF), enrolled patients will enter an up to 8 weeks screening period. Eligible patients (according to the eligibility criteria) will be treated by a single ALLOB® implantation into the delayed-union site. Once treated, patients will be followed up during 6 months with post-treatment assessments performed: at 2 weeks, 1, 3 and 6 months, respectively. During follow-up, non-responding patients (see below and section 3.2.3) could be considered as drop-out and undergo a rescue surgery, according to the judgment of the Investigator.

[REDACTED]

[REDACTED]

[REDACTED]

Experimental design	Prospective, multicentre, open, non-controlled Phase I/IIa study
Duration of study	6 months of follow-up
Delayed-union sites	Femur, tibia, fibula, humerus, ulna, radius
Treatment	ALLOB ®
Procedure	Implantation performed under anaesthesia
Study Timepoints	2 weeks, 1 month, 3 months and 6 months after treatment

Self-contained study

Data collection: Case Report Form (CRF)

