#### ***2.6.2 Inclusion Criteria***

All subjects must satisfy ALL the following criteria at study entry:

- Patient aged 18 to 80 years inclusive
- Patient diagnosed with a non-infected delayed-union fracture of a long bone (femur, tibia, fibula, humerus, ulna, radius) of minimum 3 months and maximum 7 months ( $\pm$  2 weeks) without signs of healing over the last 4 weeks at the time of screening
- Modified Radiographic Union Score (mRUS) < 10
- Global Disease Evaluation Score as assessed by the patient  $\geq$  20 mm on a Visual Analogue Scale
- Patient (or patient's legally acceptable representative) capable to provide a written, dated, and signed informed consent prior to any study procedure.

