## ALLOB-DU1 - Clinical Study Protocol

ALLOB-DU1_CSP	V 05	Author: [name]	February 02, 2017	Pg. 47/136
---------------	------	-------------	-------------------	------------

Assessing the global disease evaluation enable to avoid some bias associated with the evaluation of pain or the function of the fractured site. Indeed, another fracture nearby the target fracture, multiple fractures at the same site, nerve damages or previous surgical interventions may negatively impact the patient ability to distinguish between pain from those collateral symptoms and pain caused at the treated fracture site.

*Global Disease Evaluation (VAS)*

Response (general disease improvement) to treatment can be assessed by a Global Disease Evaluation score (visual analogue scale), which is commonly used for joint diseases (Felson *et al.*, 1997). The patient's global assessment of disease activity is a standardized and validated measure of disease (activity) status developed by the American College of Rheumatology in order to provide a simple, generic measure of health for clinical appraisal and response to treatment (ACR, Vol.57, N2, 2007; EMA, CPM/EWP/422/04, 2006).

The Global Disease Evaluation VAS defines the general health patient status corresponding at the Question "How do you feel (on a score of 0 – 100 mm where 0 mm is as good as you can feel and 100 mm extremely bad) over the last week regarding your disease (i.e., delayed-union fracture), please indicate by an "X" (between 0 mm to 100 mm) your general health status on the horizontal scale line". This information is used as a quantitative measure of health as judged by the individual respondents. The patient is asked to simply mark an "X" on the scale to indicate his/her health today (see Annex 1). The VAS score is determined by measuring in millimetres from the left hand end of the line to the point that the patient marks.

The data derived from this measurement can be analysed, as for pain, using parametric statistical techniques (Kelly, 2001). However, clinical and statistical significance are not necessarily the same, and the clinical impact on the patient and on the medical practice is a crucial factor. Therefore, a minimal clinically significant difference (minimally important difference MID) in Global Disease Evaluation as measured by VAS score has also been determined and is generally reported to range between 8 to 12 mm (Kwok and Pope, 2010; George and Pope, 2011).

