### **3.2.3 Rationale for the Choice of Clinical and Radiological Improvement Levels**

In their daily practice, orthopaedic surgeons take the decision of a new surgical intervention if signs of both clinical and radiological improvements are observed (i.e., signs of favourable evolution). This is because clinical and radiological improvements are not always correlated. This has been observed in other studies where some patients showed significant clinical improvement with limited radiological improvement or vice versa. In the present study, the same strategy of a combined clinical and radiological evaluation will help determining if a rescue surgery will be required or not.

Based on the efficacy of the treatment, Investigators will have the opportunity to switch to rescue surgery from Month 3 if the patient has not improved by at least 15% his/her global disease evaluation score (VAS) as perceived by the patient and his/her TUS or mRUS (as available) has not improved by at least 1 point.

The levels of improvements have been calculated as based on other similar impaired fracture healing trials (e.g., PREOB® on non-union fracture) and take into account standard deviation and patient variability.

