10.5.8 Interim data analysis10.5.8.1 *Efficacy Assessment*

At Month 6, the efficacy assessment will be based on:

- The patient had a rescue surgery

Or

- The Global Disease Evaluation score (VAS) as perceived by the patient has not improved by at least 25% *and* the TUS as assessed by CT scan has not increased by at least 2 points (versus baseline).

For rescue surgery, based on the efficacy of the treatment, Investigators will have the opportunity to switch to rescue surgery from Month 3 if the patient has not improved by at least 15% his/her global disease evaluation score (VAS) as perceived by the patient and his/her mRUS or TUS, as available, has not improved by 1 point.

The levels of improvements have been calculated as based on other similar impaired fracture healing trials (e.g., PREOB® on non-union fracture) and take into account standard deviation and patient variability.

10.5.8.2 *Presentation of the 2-stage design*

The main objective of this phase I/II-a non-comparative sequential design is to assess the interest presented by this new treatment without performing a comparative study that allows identifying only small differences of efficacy between the new treatment and a control, what requires a relatively high number of subjects. The principle of a sequential design is to perform the study in two or more stages in order to minimize the number of patients exposed to an ineffective treatment to conclude in a more premature way.

The most appropriate sequential method for this study is the 2-stage Fleming plan. In this design, the efficacy criterion is a binary criteria of “success/failure” type, with  $p_0$  as the superior limit of ineffectiveness (maximum value below which the new treatment is considered as being ineffective) and  $p_1$  as the inferior limit of efficacy (minimum value above which the new treatment is considered as being effective). The null and alternative test hypotheses are the following:

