**11.3 Source Data Verification**

To ensure that data in the CRF are accurate and complete, and in accordance with patient source documents and other source data (e.g., laboratory results forms), 100% of source data verification (SDV) will be performed on site by the monitor such as CRA on all data and CRFs including but not limited to patient questionnaire, SAE and pregnancy-related documents, consisting in a comparison of the source documentation data with the CRFs and other records relevant to the study. This will require direct access to all original records for each patient.

Following this SDV, any errors (discrepancies) greater than 3 mm noticed on a VAS during independent verification by/on behalf of the Sponsor (e.g., audits) must trigger appropriate corrective actions to ensure exactness of all VAS values in the study.

The process of obtaining IC and the presence on file of the signed and dated ICF will be verified for all patients screened, whether or not they were considered eligible for the study.

The back-transcription of data from the CRF into source documents is not allowed, including when discrepancies/omissions are detected by SDV.

As some data will be directly entered into the CRF, the CRF will be considered as source document for these data. The "Source Data Location List" will be completed confirming the location of the source data.

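### Is a 25% gain on the patient's global score too small a change to count as success when the baseline score is low?

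*Combined protocol and SAP*

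**What the plan says.** The success rule appears in the same form in the synopsis and in Sections 2.2.2, 10.2, 10.5.6.1 and 10.5.8.1. A patient fails after rescue surgery, or if two things are both true: "The Global Disease Evaluation score (VAS) as perceived by the patient has not improved by at least 25"%, and TUS has not increased by at least 2 points from baseline. Everyone else is a responder.

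Other places that bear on it:

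- Section 2.6.2 admits patients whose own GDE is at least "20 mm on a Visual Analogue Scale". The scale runs from 0 (best) to 100 mm (worst).
- The synopsis visit schedule uses Visit #2 "for baseline clinical assessments".
- Section 3.2.1 says of the minimally important difference (MID) for GDE that it "is generally reported to range between 8 to 12 mm".
- Section 3.2.3 gives the origin of the thresholds: "The levels of improvements have been calculated as based on other similar impaired fracture healing trials". It adds, as does Section 10.5.8.1, that they "take into account standard deviation and patient variability". Neither section shows a calculation or a link to the MID.
- Section 2.1 describes a "prospective, multicentre, open, non-controlled study".
- The lines directly after the rule in Section 10.5.6.1 are redacted, and so is the list of other efficacy endpoints in Section 10.3. Section 10 leaves the full methods to an SAP to be signed before first database lock. That SAP's text is not part of the public document.

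**The concern.** A percentage of a small number is a small number. A patient who enters at 20 mm needs only a 5 mm improvement to meet the clinical leg, and that leg is sufficient on its own if there was no rescue surgery. The protocol itself notes that clinical and statistical significance can differ, and it quotes an MID larger than 5 mm. So it appears to count as success a change that, by its own yardstick, a patient might not notice.

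The setting adds to the worry. The score is patient-reported, the study is open and there is no control arm to show how often such changes occur without treatment. The success count also drives a decision: 12 or more successes among the first 16 assessable patients stop the study for efficacy. If some successes rested on very small GDE changes, the headline rate could look firmer than it is. No analysis with a floor in mm can be seen in the readable text.

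**Working it through.** The plan states no figure for the required change in mm, so there is none to reproduce. The check is direct arithmetic.

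**Inputs.** Relative threshold 25% (Section 10.5.6.1); entry limit 20 mm (Section 2.6.2); MID 8 to 12 mm (Section 3.2.1). The 25% is read as relative to the patient's own baseline. Read as 25 points of the scale, it could not be reached by patients entering at 20 to 24 mm.

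**Required change = 0.25 × baseline.**

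| Baseline (mm) | Required gain (mm) |
|---|---|
| 20 | 5.0 |
| 24 | 6.0 |
| 30 | 7.5 |
| 32 | 8.0 |
| 40 | 10.0 |
| 48 | 12.0 |

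**Crossover baseline = MID / 0.25.** 8/0.25 = 32 mm and 12/0.25 = 48 mm. From 20 to under 32 mm the required gain is below the whole quoted range. From 32 to under 48 mm it is inside the range but below its upper end. From 48 mm it is at or above the range's upper end. Because eligibility is checked at study entry and the clinical baseline is Visit #2, up to 8 weeks later, a baseline below 20 mm is possible; at 15 mm the required gain would be 3.75 mm.

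**Who would be reclassified by a floor of 8 mm?** Four conditions must all hold: no rescue surgery; TUS gain under 2 points; baseline under 32 mm; and GDE gain of at least 25% but under 8 mm. The width of the last band is 8 − 0.25 × baseline:

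- at 20 mm: 8 − 5 = 3 mm
- at 24 mm: 8 − 6 = 2 mm
- at 30 mm: 8 − 7.5 = 0.5 mm
- at 32 mm: 0

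For a 12 mm floor the width is 12 − 0.25 × baseline: 7 mm at 20 mm, 4 mm at 32 mm, 2 mm at 40 mm and 0 at 48 mm. A patient at a low baseline who meets the TUS leg remains a success under either floor.

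**What the floors would demand.** At a 20 mm baseline, 8 mm is 8/20 = 40% improvement and 12 mm is 12/20 = 60%.

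**Interim boundary.** 12/16 = 75% meets it and 11/16 = 68.75% does not, so one reclassified patient matters if the count is exactly 12. That is true of any borderline classification and is not particular to this rule.

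**Reading error.** Section 11.3 calls for corrective action on "any errors (discrepancies) greater than 3 mm noticed on a VAS". If 3 mm were an accepted error at each visit, an unchanged 20 mm could be recorded as 23 and then 17 mm, giving 6/23 = 26% and a false success. The section does not say that. It requires source data verification of all data, questionnaires included, and uses 3 mm as a trigger for action to make all VAS values in the study exact. Nothing says that smaller errors may stand, so this example adds no weight.

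**The case for a change.** The best case for acting is that it would cost little. A few lines in the SAP, using data already collected, would show whether the conclusion survives an 8 mm or 12 mm floor, and the primary endpoint would stay as it is. The MID is the only GDE yardstick in mm that the protocol offers, and the rationale in Section 3.2.3 does not show how 25% was reached. In an uncontrolled study with a subjective score, readers may fairly want to know how many successes rest on small changes.

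Much of this stands. The arithmetic is correct, the either/or reading is correct, and the readable text never relates 25% to the MID. Three points weaken the call for a change:

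- **The yardstick is borrowed.** By title, the two works cited for the GDE MID concern Sjögren's syndrome and psoriatic arthritis. The protocol quotes the range as background and does not adopt it as a cut-off for an individual responder. Falling below it does not show that the 25% rule is wrong.
- **The information should be available anyway.** Section 13.1 commits the study report to individual patient data listings, and at most 32 patients are treated. With baseline and Month 6 GDE, TUS and rescue status listed, a reader can apply any floor. At the interim, the DSMB assesses the efficacy endpoints itself (Sections 8.3.4 and 10.10).
- **Absence cannot be shown.** A sensitivity analysis would naturally sit in the redacted lines after the rule, or in the SAP. That it cannot be seen is not evidence that it was not planned.

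**Conclusion.** No change to the plan follows. For a patient without rescue surgery and with a TUS gain under 2 points, a 25% GDE gain is sufficient for success. That is 5 mm at the entry limit, less than the quoted 8 to 12 mm for baselines under 32 mm, and less than 12 mm for baselines under 48 mm.

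This is a defensible trade-off. A percentage threshold is a legitimate choice, and Section 3.2.3 explains why clinical and radiological gains are judged together: they do not always move in step. Section 10.5.1.2 says that in this pilot a missed effect may be more serious than a false lead, whereas a floor would ask low-baseline patients for 40% or 60% improvement.

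The extra analyses would leave the primary definition and every stopping boundary untouched, with no stated consequence if they disagreed. A statistician who wants to report how many successes rest on a GDE gain of at least 25% but under 8 or 12 mm can do so, and one who does not has left no error in the plan.

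The size of the effect cannot be stated, since the documents give no baseline GDE distribution; it may be nil. The conclusion assumes that 25% is relative to the patient's baseline and that the listings include GDE, TUS and rescue status.
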